2.11. Subject Withdrawals

Subject withdrawals will be summarized in a disposition table for all subjects by treatment. The reasons for discontinuation will also be tabulated. Withdrawals due to AEs will be tabulated as discussed in the Adverse Event section above. A listing of the subjects who withdrew due to an AE will be presented as well as a listing of the subjects' completion and/or discontinuation status.

2.12. Protocol Deviations

Protocol deviations will be displayed in a data listing as provided by the clinical team.

2.13. Computer Systems and Packages Used for Statistical Analyses

SAS® version 9.4 or higher on the Microsoft Windows 7 64 bit platform will be used for all analyses. All computations will be performed using SAS®. The exact form of the various algorithms will be the SAS® defaults. The output from any SAS® procedure will be used in the tables using SAS® macros.

3. Data Listing Shells

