2.1. General Statistical Methods

Efficacy summaries will be provided for the Intention to Treat and Per Protocol Populations. Safety summaries will be provided for the Safety Population.

Descriptive statistics (N, arithmetic means, SD, minimum, median, maximum) for all continuous values and frequency tables for categorical variables will be created. With regard to primary and secondary objectives as descriptive statistical evaluation, absolute and relative frequencies of number of observations will be presented together with 95% confidence intervals on the proportion of success and the difference compared to Vehicle Cream.

If the method to handle missing observations is not explicitly defined (i.e. Percent Change from Baseline in Actinic Keratosis Lesion Count), two principles will be applied to adjust for missing observations: last observation carried forward (LOCF) and multiple imputations (MI). Last observation carried forward will be derived in the analysis datasets while the multiple imputations method will be performed using SAS procedures PROC MI and PROC MIANALYZE.

If there are at least 5 observations in each cell in the 2 x 2 table (when comparing treatment groups to Vehicle), the Pearson's Chi Square test will be used. If there are not at least 5 observations in each cell in the 2 x 2 table (when comparing treatment groups to Vehicle), the Fisher's exact test will be used.

A Documentation of Statistical Decisions will be created, reviewed and signed (with appropriate signatures) prior to database lock. This document will document:

- On a subject level, which populations the subject is included in and reason for exclusion if a subject is excluded from a population.
- The details of any decision made (i.e. how data is handled in the analysis or the addition of any outputs) based on the actual data collected.
- Any known issues with the data quality and how that data is handled in the analysis, and
- Any other unexpected findings that require documentation prior to database lock.

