2.6. Efficacy

Primary endpoint

For statistical assessment of the primary endpoint with a significance level of 0.05 the following underlying hypotheses are used:

$H_0: p_1 \leq p_2$ vs. $H_a: p_1 > p_2$

Where p_1 is the treatment effect of 2.5% DFD-07 (celecoxib) Cream twice daily and p_2 is the treatment effect of the Vehicle Cream preparation.

Secondary endpoints

For statistical assessment of all product comparisons after certain period of treatment (i.e. at Visits 3, 4, 5 and 6) with a significance level of 0.05, the following underlying hypotheses are used:

$H_0: p_1 \leq p_2$ vs. $H_a: p_1 > p_2$

Where p_1 is the treatment effect of 1.25% or 2.5% DFD-07 (celecoxib) Cream once daily and p_2 is the treatment effect of the Vehicle Cream preparation.

For the percent change from baseline in AK lesion counts, the Mann-Whitney U-test (Wilcoxon rank sum test) will be used to test for treatment differences compared to the Vehicle Cream preparation at a significance level of 0.05.

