2.8. Sample Size and Power Considerations

The sample size estimation of this trial is based on the assumption that the Active product exhibits a complete clearance of the AK lesions in 45% of the subjects, while the Vehicle does so in 20% of the subjects (a difference of 25% between active and Vehicle treatment groups). Assuming a power of 80% and α of 0.05, in order to demonstrate the statistical significance of such an effect difference, 54 patients per treatment group would be needed.

Considering the exploratory dose-response character of the trial, and assuming a drop-out rate of 10%, 60 subjects need to be recruited in each treatment group. With 4 treatment groups in the study, it is planned to recruit approximately 240 subjects in the study.

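### The SAP names no method for its 95% intervals on clearance rates and differences; if the software default is Wald, single-arm and small-subgroup intervals will be unreliable, though the primary contrast is not

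*SAP*

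**What the plan says.** SAP 2.1 (General Statistical Methods) promises, for the primary and secondary objectives, "95% confidence intervals on the proportion of success and the difference compared to Vehicle Cream". It places them under descriptive evaluation and gives no formula or named method. The same section does specify the tests: Pearson's chi-square when every cell of the 2 x 2 table holds at least 5 subjects, otherwise Fisher's exact test. So the tests are fixed and the intervals are not.

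The only rule that reaches the intervals is in SAP 2.13: "The exact form of the various algorithms will be the SAS® defaults". Table shells are held in a separate file (SAP 4.3), which is not among the documents.

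Complete clearance is tabulated by visit and again by visit within seven subgroup splits, including race and ethnicity (SAP 2.3 and 4.1). SAP 2.6 states a significance level of 0.05 and writes the hypotheses in one direction only, active better than Vehicle. Neither SAP 2.6 nor the sample-size section ("Assuming a power of 80% and α of 0.05") says whether the p-value is one- or two-sided.

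**The concern.** Regimen-by-visit estimates with their intervals are a main product of a dose-response trial that the SAP itself calls exploratory. If the default is the Wald interval (estimate plus or minus 1.96 unpooled standard errors), its behaviour worsens as rates approach zero or samples become small. A single-arm interval then covers too rarely, and with no clearances it reads 0% to 0%. The interval for a difference also uses a different standard error from the Pearson test, so one table can show an interval above zero beside a non-significant p-value. Low clearance at Weeks 4 and 8 and thin subgroups are where readers would meet this.

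**Working it through.** **Inputs**
- Planned rates, stated for active treatment against Vehicle (SAP 2.8): "exhibits a complete clearance of the AK lesions in 45% of the subjects, while the Vehicle does so in 20% of the subjects".
- Size: "54 patients per treatment group would be needed", and "assuming a drop-out rate of 10%, 60 subjects need to be recruited in each treatment group" (SAP 2.8).
- Low-rate scenario: 14% against 4%, the lowest pair in Table 1 of the protocol introduction. It comes from a different drug, diclofenac gel, after 30 days of treatment.
- Assumptions: the default is Wald; subgroup sizes, which the documents do not give, run from 10 to 30 per arm.

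**The plan's own figure.** With pooled variance, no continuity correction and a two-sided 0.05, the mean rate is 0.325:

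n = [1.96 x sqrt(2 x 0.325 x 0.675) + 0.8416 x sqrt(0.45 x 0.55 + 0.20 x 0.80)]^2 / 0.25^2 = (1.298 + 0.537)^2 / 0.0625 = 53.9, so 54; and 54 / 0.90 = 60.

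The same formula with a one-sided 0.05 gives 43. The plan's 54 therefore matches a two-sided test, while the hypotheses are written one-sided.

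**Coverage of the interval for the difference.** All pairs of binomial outcomes were enumerated exactly. Wald is d +/- 1.96 x sqrt[p1(1-p1)/n + p2(1-p2)/n]. Newcombe combines the two single-arm Wilson limits.

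| Rates | n per arm | Wald | Newcombe |
|---|---|---|---|
| 45% / 20% | 60 | 94.8% | 94.9% |
| 45% / 20% | 54 | 94.7% | 95.0% |
| 14% / 4% | 60 | 94.4% | 96.4% |
| 45% / 20% | 30 | 93.9% | 95.0% |
| 45% / 20% | 15 | 92.8% | 94.7% |
| 45% / 20% | 10 | 91.0% | 94.9% |
| 14% / 4% | 30 | 91.5% | 97.7% |
| 14% / 4% | 15 | 88.8% | 98.0% |
| 14% / 4% | 10 | 77.3% | 99.4% |

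With full arms of 60 the difference holds up even at 14% against 4%. It weakens when the sample is small.

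**Coverage of a single-arm interval, n = 60**

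| Rate | Wald | Wilson |
|---|---|---|
| 45% | 94.9% | 94.9% |
| 20% | 92.2% | 96.6% |
| 14% | 91.9% | 94.1% |
| 4% | 91.1% | 96.7% |
| 5% | 80.6% | 97.0% |

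The irregular order of the last two rows is a discreteness effect of the binomial. The 5% rate is a scenario, not a figure from the plan.

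**Zero width.** A single-arm Wald interval collapses at zero events. At a 4% rate the chance is 0.96^60 = 8.6% with 60 subjects and 0.96^15 = 54% with 15. Wilson at 0/60 gives 0% to 3.84 / (60 + 3.84) = 6.0%. The difference interval collapses only when both arms have no variance: 0.86^60 x 0.96^60 = 0.00001 at 14% against 4% with 60 per arm, but 0.86^10 x 0.96^10 = 14.7% with 10 per arm.

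**Agreement with the planned test.** Take 25/60 against 15/60, so d = 0.1667.
- Wald: the unpooled standard error is 0.0847, and the interval is 0.06 to 33.3 points.
- Pearson: the pooled standard error is 0.0861, z = 1.936, two-sided p = 0.053.
- Newcombe: the lower limit is -0.2 points, in line with the two-sided test.

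Frequency of disagreement with the SAP's Pearson/Fisher rule taken as two-sided, n = 60:

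| Rates | Wald | Newcombe | Interval inverting Pearson exactly |
|---|---|---|---|
| 45% / 20% | 0.7% | 0.06% | 0% |
| 14% / 4% | 18.3% | 10.5% | 14.8% |

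At 14% against 4% the rule selects Fisher in 91% of trials, so most of that row reflects Fisher's conservatism. For example, 12/60 against 4/60 has Fisher p = 0.058, yet the Wald lower limit is 1.4 points and Newcombe's is 1.0.

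**Sidedness.** If the test is run one-sided at 0.05, as the hypotheses are written, then at 45% against 20% with 60 per arm it is significant while the 95% Wald interval includes zero in 5.5% of trials. That is about eight times the 0.7% above (5.5 / 0.7 = 7.9), and changing the interval method would not cure it.

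**The case against.** The strongest reply is that this is a reporting detail. The documents never mention Wald, the table shells may name a method, the SAP presents the intervals as descriptive, and the primary test, sample size and power do not depend on them. All of that stands. It lowers the importance but does not supply the missing method.

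Three stronger readings are tempting, and the documents do not support them.
- A reader might infer that the primary Week 16 interval is unreliable because low clearance is expected. The plan expects 45% and 20%, where Wald and Newcombe differ by about 0.1 point of coverage.
- A reader might infer that the interval for a difference collapses whenever one arm has no clearances. It does not: 5/60 against 0/60 gives 1.3 to 15.3 points. Collapse at zero events belongs to single-arm intervals, and to differences only if both arms lack variance.
- A reader might attribute the 18.3% disagreement at 14% against 4% to Wald. Most of it comes from Fisher's test, and 10.5% remains with Newcombe.

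The choice among score intervals is also partly preference, and Newcombe over-covers at low rates in small samples (99.4% at 14% against 4% with 10 per arm).

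**Conclusion.** A minor specification gap that is worth closing. It is certain that the SAP text supplied names no method for the intervals it promises. That the default is Wald is an assumption about software. If it is right, the primary difference is sound. The affected outputs are single-arm intervals (92.2% coverage at the planned Vehicle rate of 20%, 80.6% at 5%), early visits with low clearance, mainly through those single-arm intervals, and subgroup tables (91.0% at 45% against 20% and 77.3% at 14% against 4%, both at an assumed 10 per arm). Real subgroup sizes and early clearance rates are unknown, so these figures show the range and are not forecasts. At the planned rates, the unstated sidedness of the test causes more conflict between test and interval than the Wald formula does.

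**What to change.** Add to SAP 2.1, as an explicit exception to SAP 2.13: differences from Vehicle use the Miettinen-Nurminen score interval (or Newcombe's), and single proportions use the Wilson interval. Make the table shells match. In SAP 2.6 state whether the 0.05 is one- or two-sided. A two-sided 0.05 agrees with the sample-size figure of 54 and with a 95% interval; if a one-sided 0.05 is intended, say which interval level corresponds to it.

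The cost is a sentence or two in the SAP and an option in the code. Sample size and power do not change. Some intervals become slightly wider or conservative at very low rates. Where the Fisher branch applies, some disagreement with the interval will remain, and a table footnote should say so.

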3.1. Data Listings Table of Contents

The following post-text listings will be generated.

Listing Number	Listing Title
16.1.7	Randomization Schedule
16.2.1	Subject Completion / Discontinuation
16.2.2	Protocol Deviations
16.2.3	Study Populations
16.2.4.1	Demographics and Baseline Characteristics
16.2.4.2	Subject Eligibility and Informed Consent
16.2.4.3	Substance Use
16.2.4.4	Actinic Keratosis History
16.2.4.5	Medical History / Surgical History / Procedures
16.2.4.6	Prior and Concomitant Medications
16.2.4.7	Non-Drug Treatment History
16.2.5.1	Study Drug Accountability
16.2.5.2	Study Drug Exposure
16.2.6.1	Actinic Keratosis Lesion Counts
16.2.6.2	Complete and Partial Clearance
16.2.7.1	Adverse Events
16.2.7.2	Adverse Events Leading to Discontinuation of Study
16.2.7.3	Serious Adverse Events
16.2.7.4	Adverse Events Related to Study Procedures Prior to Study Product Administration
16.2.8.1	Laboratory Results - Hematology
16.2.8.2	Laboratory Results - Chemistry
16.2.8.3	Laboratory Results - Urinalysis
16.2.9.1	Safety and Local Tolerability Evaluation
16.2.9.2	Vital Signs
16.2.9.3	Electrocardiogram Results
16.2.9.4	Physical Examination

3.2. Data Listings

All subjects and all data will be presented in the listings. The listings will be sorted by treatment and subject number with page breaks between treatments.

4. Summary Table and Figure Shells

4.1. Post-text Table of Contents

The following post-text tables will be generated.

Table Number	Table title
14.1.1.1	Summary of Subject Disposition – Intention-to-Treat Population
14.1.1.2	Summary of Subject Disposition – Safety Population
14.1.1.3	Summary of Subject Disposition – Per Protocol Population
14.1.2.1	Summary of Demographics and Baseline Characteristics – Intention-to-Treat Population
14.1.2.2	Summary of Demographics and Baseline Characteristics – Safety Population
14.1.2.3	Summary of Demographics and Baseline Characteristics – Per Protocol Population
14.1.3.1	Summary of Actinic Keratosis History – Safety Population
14.1.3.2	Summary of Medical History – Safety Population
14.1.4.1	Summary of Prior Medications – Safety Population
14.1.4.2	Summary of Concomitant Medications – Safety Population
14.1.5.1	Summary of Extent of Exposure – Intention-to-Treat Population
14.1.5.2	Summary of Extent of Exposure – Safety Population
14.1.5.3	Summary of Extent of Exposure – Per Protocol Population
14.2.1.1	Proportion of Subjects with Complete Clearance by Visit – ITT Population
14.2.1.2	Proportion of Subjects with Complete Clearance by Visit – PP Population
14.2.1.3	Proportion of Subjects with Complete Clearance by Visit – Based on Age – ITT Population
14.2.1.4	Proportion of Subjects with Complete Clearance by Visit – Based on Median Age – ITT Population
14.2.1.5	Proportion of Subjects with Complete Clearance by Visit – By Gender – ITT Population
14.2.1.6	Proportion of Subjects with Complete Clearance by Visit – By Race – ITT Population
14.2.1.7	Proportion of Subjects with Complete Clearance by Visit – By Ethnicity – ITT Population

Table Number	Table title
14.2.1.8	Proportion of Subjects with Complete Clearance by Visit – By Location of Treated Lesion(s) – ITT Population
14.2.1.9	Proportion of Subjects with Complete Clearance by Visit- By Previous AK treatment –ITT population
14.2.2.1	Proportion of Subjects with Partial Clearance by Visit – Last Observation Carried Forward - ITT Population
14.2.2.2	Proportion of Subjects with Partial Clearance by Visit – Last Observation Carried Forward - PP Population
14.2.2.3	Proportion of Subjects with Partial Clearance by Visit – Based on Age – Last Observation Carried Forward - ITT Population
14.2.2.4	Proportion of Subjects with Partial Clearance by Visit – Based on Median Age – Last Observation Carried Forward - ITT Population
14.2.2.5	Proportion of Subjects with Partial Clearance by Visit – By Gender – Last Observation Carried Forward - ITT Population
14.2.2.6	Proportion of Subjects with Partial Clearance by Visit – By Race – Last Observation Carried Forward - ITT Population
14.2.2.7	Proportion of Subjects with Partial Clearance by Visit – By Ethnicity – Last Observation Carried Forward - ITT Population
14.2.2.8	Proportion of Subjects with Partial Clearance by Visit – By Location of Treated Lesion(s) – Last Observation Carried Forward - ITT Population
14.2.2.9	Proportion of Subjects with Partial Clearance by Visit- By Previous AK treatment – Last Observation Carried Forward - ITT population
14.2.3.1	Proportion of Subjects with Partial Clearance by Visit – Multiple Imputation Method - ITT Population
14.2.3.2	Proportion of Subjects with Partial Clearance by Visit – Multiple Imputation Method - PP Population
14.2.3.3	Proportion of Subjects with Partial Clearance by Visit – Based on Age – Multiple Imputation Method - ITT Population
14.2.3.4	Proportion of Subjects with Partial Clearance by Visit – Based on Median Age – Multiple Imputation Method - ITT Population
14.2.3.5	Proportion of Subjects with Partial Clearance by Visit – By Gender – Multiple Imputation Method - ITT Population
14.2.3.6	Proportion of Subjects with Partial Clearance by Visit – By Race – Multiple Imputation Method - ITT Population
14.2.3.7	Proportion of Subjects with Partial Clearance by Visit – By Ethnicity – Multiple Imputation Method - ITT Population

Table Number	Table title
14.2.3.8	Proportion of Subjects with Partial Clearance by Visit – By Location of Treated Lesion(s) – Multiple Imputation Method - ITT Population
14.2.3.9	Proportion of Subjects with Partial Clearance by Visit- By Previous AK treatment – Multiple Imputation Method - ITT population
14.2.4.1	Percent Change from Baseline in Actinic Keratosis Lesion Count by Visit – Last Observation Carried Forward - ITT Population
14.2.4.2	Percent Change from Baseline in Actinic Keratosis Lesion Count by Visit – Last Observation Carried Forward - PP Population
14.2.4.3	Percent Change from Baseline in Actinic Keratosis Lesion Count by Visit – Based on Age – Last Observation Carried Forward - ITT Population
14.2.4.4	Percent Change from Baseline in Actinic Keratosis Lesion Count by Visit – Based on Median Age – Last Observation Carried Forward - ITT Population
14.2.4.5	Percent Change from Baseline in Actinic Keratosis Lesion Count by Visit – By Gender – Last Observation Carried Forward - ITT Population
14.2.4.6	Percent Change from Baseline in Actinic Keratosis Lesion Count by Visit – By Race – Last Observation Carried Forward - ITT Population
14.2.4.7	Percent Change from Baseline in Actinic Keratosis Lesion Count by Visit – By Ethnicity – Last Observation Carried Forward - ITT Population
14.2.4.8	Percent Change from Baseline in Actinic Keratosis Lesion Count by Visit – By Location of Treated Lesion(s) – Last Observation Carried Forward - ITT Population
14.2.4.9	Percent Change from Baseline in Actinic Keratosis Lesion Count by Visit- By Previous AK treatment – Last Observation Carried Forward - ITT population
14.2.5.1	Percent Change from Baseline in Actinic Keratosis Lesion Count by Visit – Multiple Imputation Method - ITT Population
14.2.5.2	Percent Change from Baseline in Actinic Keratosis Lesion Count by Visit – Multiple Imputation Method - PP Population
14.2.5.3	Percent Change from Baseline in Actinic Keratosis Lesion Count by Visit – Based on Age – Multiple Imputation Method - ITT Population
14.2.5.4	Percent Change from Baseline in Actinic Keratosis Lesion Count by Visit – Based on Median Age – Multiple Imputation Method - ITT Population
14.2.5.5	Percent Change from Baseline in Actinic Keratosis Lesion Count by Visit – By Gender – Multiple Imputation Method - ITT Population
14.2.5.6	Percent Change from Baseline in Actinic Keratosis Lesion Count by Visit – By Race – Multiple Imputation Method - ITT Population
14.2.5.7	Percent Change from Baseline in Actinic Keratosis Lesion Count by Visit – By Ethnicity – Multiple Imputation Method - ITT Population

Table Number	Table title
14.2.5.8	Percent Change from Baseline in Actinic Keratosis Lesion Count by Visit – By Location of Treated Lesion(s) – Multiple Imputation Method - ITT Population
14.2.5.9	Percent Change from Baseline in Actinic Keratosis Lesion Count by Visit- By Previous AK treatment – Multiple Imputation Method - ITT population
14.2.6.1	Proportion of Subjects with Local Skin Reactions by Visit – ITT Population
14.2.6.2	Proportion of Subjects with Local Skin Reactions by Visit – PP Population
14.2.6.3	Proportion of Subjects with Local Skin Reactions by Visit – Based on Age – ITT Population
14.2.6.4	Proportion of Subjects with Local Skin Reactions by Visit – Based on Median Age – ITT Population
14.2.6.5	Proportion of Subjects with Local Skin Reactions by Visit – By Gender – ITT Population
14.2.6.6	Proportion of Subjects with Local Skin Reactions by Visit – By Race – ITT Population
14.2.6.7	Proportion of Subjects with Local Skin Reactions by Visit – By Ethnicity – ITT Population
14.2.6.8	Proportion of Subjects with Local Skin Reactions by Visit – By Location of Treated Lesion(s) – ITT Population
14.2.6.9	Proportion of Subjects with Local Skin Reactions by Visit- By Previous AK treatment –ITT population
14.3.1.1	Summary of Treatment Emergent Adverse Events – Safety Population
14.3.1.2	Summary of Treatment Emergent Adverse Events by Severity – Safety Population
14.3.1.3	Summary of Treatment Emergent Adverse Events by Relationship – Safety Population
14.3.1.4	Summary of Adverse Events Leading to Discontinuation – Safety Population
14.3.1.5	Summary of Serious Adverse Events – Safety Population
14.3.2.1	Summary of Lab Parameters – Hematology – Safety Population
14.3.2.2	Summary of Lab Parameters – Chemistry – Safety Population
14.3.2.3	Summary of Lab Parameters – Urinalysis – Safety Population
14.3.3	Summary of Safety and Local Tolerability Evaluation – Safety Population
14.3.4	Summary of Vital Signs – Safety Population

4.2. Post-text Figures Tables of Contents

Figure Number	Figure title
14.2.1	Complete Clearance – Intention-to-Treat Population
14.2.2	Partial Clearance - Intention-to-Treat Population
14.2.3	Percent Change from Baseline in Actinic Keratosis Lesion Count - Intention-to-Treat Population

4.3. Table Shells

The table shells can be found in a separate zipped file. The following number of decimal places will be used when presenting summary statistics:

- N to 0 decimal places
- Minimum and maximum to 0 or 1 decimal places, depending on how the raw data was recorded
- Means and medians to 1 decimal place. Standard deviations to 2 decimal places
- Percentages to 1 decimal place

The precision may be changed for individual endpoints as needed.
